Title: Post-Prandial Liver Glucose Metabolism in Polycystic Ovarian Syndrome (PCOS) and understanding Standard of Care Medications

Version Date: 8/17/2017

NCT03041129

COMIRB Protocol

COLORADO MULTIPLE INSTITUTIONAL REVIEW BOARD
[name] [contact] [contact]

Project Title: Post-Prandial Liver Glucose Metabolism in Polycystic Ovarian Syndrome (PCOS) and understanding Standard of Care Medications

Version Date: 8/17/2017

Principal Investigator: [name] [name], PhD

I. Hypotheses and Specific Aims:

HYPOTHESIS:

Obese girls with hepatic steatosis (HS) will have hepatic glucose metabolism that is upregulated towards de novo lipogenesis (DNL) via multiple intrahepatic pathways, compared to PCOS without HS and obese controls without HS. HS will be related to relative post-prandial hyperglycemia. Post-prandial hyperglycemia will be made worse or remain unchanged with oral contraceptives and better with metformin.

Specific Aims:

Aim 1: In obese girls with PCOS, post-prandial hepatic substrate metabolism will differ by HS status and treatment regimen and can be assessed with just an oral tracer protocol combined with NMR isotopomer analysis.

Hypothesis: Girls with HS will have upregulated post-prandial hepatic non-glycogenic metabolism compared to those without HS. This will be unchanged by oral contraceptives, and decreased with metformin.

Rationale: A marker of whole body DNL was increased in girls with HS, and preliminary work from my K23 project indicates that direct measures of DNL are elevated, but upstream alterations in intrahepatic metabolism are unclear. Oral contraceptives do not mitigate metabolic risk, whereas metformin decreases HS.

Methods: A 6.5 hour OGTT with an oral U-C₁₃glycerol tracer will be paired with NMR isotopomer analysis of serum samples to describe flux through the hepatic pentose phosphate pathway, TCA cycle and DNL pathways in girls with PCOS receiving lifestyle only, metformin or oral contraceptive treatment, and obese girls with regular menses receiving lifestyle therapy.

Aim 2: Describe the optimal timing for identifying metabolomics profiles associated with risk for T2D and HS.

Hypothesis: Metabolomics profiles between girls with HS and worse IR will differ the most between 3-6 hours.

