WatchPAT: During the hospital overnight stay, trained study staff will place the WatchPAT sleep monitor. The primary measures will be for oxygen saturation and apnea hypopnea index (AHI). Each participant will wear the watch with a one-time use finger cuff as recommended by the FDA. The watch will be placed by 8 PM, and will be removed the following morning.

Details of Stable Glycerol Isotope Tracer studies with an OGTT: After the overnight fast at approximately 730AM, subjects will consume a 75 grams glucose load with an additional 25 grams of fructose to stimulate hepatic de novo lipogenesis. An 3 hours later, following consumption of the glucola/fructose mixture, 50 mg/kg of an oral ¹³C-glycerol tracer will be consumed mixed with water. Analysis of serum glucose isotopomers will be performed by our collaborator [name] at UT Southwestern, using NMR isopomer analysis and pathway modeling software. Lipolysis will be modeled using FFA concentrations and whole body IR by a time modified version of the Matsuda model.

Using a metabolic cart and hood, resting VO₂ (ml/kg/min) and VCO₂ (ml/kg/min) measurements (REE) will be collected the morning of the OGTT prior to the start of the OGTT, as well as 30 min after the start of the OGTT, 3 hours and 30 min after the start of the OGTT and 5 hours and 30 min after the start of the OGTT. This is required to determine what portion of ingested carbohydrates are subject to oxidative and non-oxidative glucose disposal⁴⁵.

Study diet: Variations in diet, activity and circadian rhythms affect metabolism ³⁴. Therefore, OGTT studies will be performed in the AM fasting, in the follicular phase where possible, preceded by 3 days of no strenuous physical activity and 2 meals of a fixed macronutrient, high carbohydrate (65% carbohydrate, 20% fat, 15% protein), fixed grams of fructose, calculated as Females: ([8.365 (weight in kg) + 465 (height in m) + 200] X Activity Factor x 1.25), dinner and snack provided by the Colorado CCTSI metabolic kitchen (similar to our previous studies³⁴). 1.25 x weight maintenance was chosen as this as most similar to our subjects food consumption based on pilot subject's food frequency questionnaires and optimal for detection of hepatic glucose Ra ⁴⁶.

Purpose for lab test to be drawn:

OGTT Labs	Purpose
Lipids and glycerol samples for tracer analysis	Determination of hepatic metabolism flux
Glucose	Determination of IR
Insulin	Determination IR
FFA	Measure of lipolysis

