Glycerol	Measure of lipolysis
Glucagon	Gut hormone known to influence hepatic IR
GLP-1	Gut hormone known to influence hepatic IR
CRP	Marker of inflammation, known to effect IR
Leptin	Gut hormone known to influence hepatic IR
Adiponectin	Adipokine thought to influence adipose IR
Estradiol	Known to effect IR and HDNL
Progesterone	Demonstrate the subject is in the follicular phase of cycle, required for publication
Metabolomics	Correlation with hepatic metabolism flux
1 sample for genetic analysis	Measure for common polymorphisms associated with hepatic steatosis ^{47,48}
Stored blood	Future markers of glucose and fat metabolism, CVD or hormones related to PCOS

Purpose for questionnaires being done:

Questionnaire	Description	Study Validity
Adolescent Sleep Hygiene Scale	Measurement of sleep patterns/habits	Cronbach's alpha ranges from .46-.74; total scale alpha = .80 LeBourgeois et al. 2005. The Relationship Between Reported Sleep Quality and Sleep Hygiene in Italian and American Adolescents
Center for Epidemiological Studies Depression (CES-D)	Measuring for depression	See Table 3 below, adapted from: Stockings et al. 2015. Symptom screening scales for detecting major depressive disorder in children and adolescents: A systematic review and meta-analysis of reliability validity and diagnostic utility
Cleveland Adolescent Sleepiness Questionnaire	Measurement of sleepiness during a typical week	alpha = .89 Spilsbury et al. 2007. The Cleveland Adolescent Sleepiness Questionnaire: A New Measure to Assess Excessive Daytime Sleepiness in Adolescents
SDQ: Strengths and Difficulties Questionnaire	Behavioral screening questionnaire	The internal reliability of the various self report scales was assessed using Cronbach's alpha coefficient. This was 0.82 for the total difficulties, 0.75 for emotional symptoms, 0.72 for conduct problems, 0.69 for hyperactivity, 0.65 for prosocial behaviour, and 0.61 for peer problems. Goodman et al. 2003. The Strengths and Difficulties Questionnaire: a pilot study on

		the validity of the self-report version
Sleep Disturbances Scale for Children	Gain understanding of sleep-wake rhythm and any problems in sleep behavior	Internal consistency ranged from .71-.79 test-retest reliability $r = .71$ Bruni et al. 1996. The Sleep Disturbance Scale for Children (SDSC) Construction and validation of an instrument to evaluate sleep disturbances in childhood and adolescence

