Justification/Minimization: These studies involve sampling blood at multiple time points. Thus, an IV is needed, so as to avoid multiple needle sticks. These studies are focused on measured rates of change which necessitates the sampling of the same test over time. Proper sterile technique will be used with blood draws and IV placement to decrease the infection risk. EMLA cream will be used if subject desires to minimize pain of IV.

3. Oral Glucose Tolerance Test (OGTT):

Description: An OGTT will be performed with multiple blood draws over 6.5 hours. The purpose of the OGTT is to provide a controlled oral stimulus to effect changes in lipolysis and hepatic glucose release. Subjects will also drink a glucose+fructose drink as part of the liver spectroscopy.

Risk: The subjects rarely experience nausea within 15 min of consuming the drink, however, the amount of carbohydrate is very similar to a large soda, which is regularly consumed by this patient population.

Justification/Minimization: A standard oral challenge is needed to study lipogenesis, lipolysis and gluconeogenesis in the fed state. We have chosen to start with a standard glucose and fructose load, to simplify the mathematical modeling. Dynamic carbohydrate metabolism in youth is made more relevant by the recently reported TODAY study, showing a decline in beta cell function in youth with newly diagnosed type 2 diabetes that was much more rapid than what has been reported in adults, and not prevented by metformin in the majority of the youth⁴⁹. Our team of investigators, CTRC pediatric research nursing staff and physicians are well experienced with the OGTT blood draw procedure. A floor nurse located on the 9th floor of CHC will be available during our inpatient visits and patients will be distracted by TV or other similar means during the OGTT, to minimize queasiness.

4. Stable Isotope Studies:

Description: Oral stable isotope tracer of glycerol will be utilized to determine rates of intrahepatic substrate flux. These are substances normally present or produced in the body, and thus pose no more risk than typical glucose infusions. Measurements of these metabolic processes are only able to be made with the utilization of stable isotope tracers.

Risk: We are utilizing an isotope which already exists in all humans, but are simply increasing the percentage. We are only giving this medication orally. These are NOT radioactive substances.

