The protocol as described includes the entire subject set, which allow for comparisons between obese girls with and without PCOS. OGTT with an oral tracer will be conducted in all subjects. The specific points that are to be evaluated are listed below:

- 1) OGTT with glycerol tracers
 - a. Purpose: Develop an oral stimulus model to assess hepatic substrate flux
 - i. Question 1. Is 6.5 hours post oral load long enough to model hepatic and adipose insulin sensitivity?
 1. Rationale: In our current study (14-0542), we have found that 6 hours are required for metabolites to return to normal, we do not anticipate this to change greatly with the addition of the glycerol tracer.
 2. Measurement. Serum glucose and insulin will be measured post-glucose load for 6.5 hours in the first 6 subjects. If 6.5 hours post glucose values are within 20 mg/dL for glucose and 20 IU/mL for insulin relative to baseline values, 6.5 hours will be considered sufficient.
- 2) Measurement of Hepatic Substrate flux in youth.
 - a. Purpose: Optimize a model to asses hepatic substrate flux in youth looking at shifts from pentose phosphate pathway (PEP), TCA cycle and fatty acid synthesis
 - i. Rational: utilizing an oral glycerol model with NMR isotopomer analysis is a newer technique. It has not been validated in youth.
 - ii. Measurement: NMR isotopomer analysis with pathway flux calculations and modeling
 - iii. Revision plan if model not correct: 1) increase the amount of tracer given 2) increase the frequency of blood draws in the later sampling period.

Overall Project Limitations:

- 1) Subject recruitment is always a potential concern, but is minimized by a streamlined recruitment system and experience with this population; the previous, more intensive study is well tolerated in youth and enrolled faster than projected. In addition, we had >100 new PCOS referrals to our pediatric endocrinology department in 2013 alone, and the PI has a clinic specifically for girls with PCOS.
- 2) Subject drop-out: We expect reasonably good completion rates due to the non-invasive nature of the two study visits and our low dropout rate in our previous studies in control and PCOS adolescents using similar procedures.

V. Data Management and Security Plan

Data Entry

Data will be entered from paper forms. Once forms are completed, verified and corrected for inconsistencies, they will be manually entered at our site using a computerized data management system (Redcap).

Edit Checks

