Secondary outcomes include a Pearson correlation test of potentially related variables followed by targeted multiple regression to assess the relationship between hepatic fat and adipose IR, PEP, TCA, TG synthesis pathways.

Non-Isotope OGTT calculations: The Matsuda model of IR will be used but adapted for the 6.5 hour OGTT, and B-cell function [insulinogenic index ($\Delta I30/\Delta G30$) and ($\Delta C30/\Delta G30$) and disposition index ($1/I_{Fasting} \times \Delta I30/\Delta G30$) and ($1/C_{Fasting} \times \Delta C30/\Delta G30$) will be calculated^{38,49,51,52}.

Differences between groups will be evaluated with and without controlling for activity and sleep status.

Fitting glucose and glycerol concentrations curves: Using computed data points, glycerol and glucose concentrations will be fitted with an appropriate model. In control subjects, concentration typically shows 3 phases in OGTT ⁵³. Cubic polynomial, piecewise-linear, spline, and dynamic models have been used for fitting Ra in previous work^{54,55}. We will assume a cubic polynomial model; we will validate estimates obtained with the cubic polynomial model by computing comparable estimates using at least one other model form. In previous work comparing different models (piecewise-linear, cubic polynomial, dynamic), results have been relatively unaffected by choice of model. If we find that this is not the case for our data, then we would certainly consider the advantages of adopting a more complex approach, such as the state-space, for describing concentration changes.

Metabolomics data: Differences in targeted metabolic concentrations will be compared between groups, after appropriate cleaning of the data, as performed by the processing site. Changes in metabolites over time will be compared between groups, to determine the times that demonstrate the largest differences. Results will also be compared to isotopomer results, to see if a metabolomics endpoint can yield similar information to the isotopomer analysis.

Gut Microbiota: The microbiota profile is entirely exploratory, and will be related to status of hepatic steatosis and 2 hour glucose status of impaired glucose tolerance or not.

VIII. Summarize Knowledge to be Gained:

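### Glycerol is listed as a lipolysis marker and curve-fitted, but every participant swallows glycerol at 3 h and the plan does not separate ingested from endogenous glycerol

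*Combined protocol and SAP*

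**What the plan says.** - **Role of glycerol.** In the OGTT lab table (Section III.C, Visit 3), the purpose given for serum glycerol is "Measure of lipolysis". FFA carries the same purpose.
- **Curve fitting.** Section VII, under the fitting of glucose and glycerol curves: "Using computed data points, glycerol and glucose concentrations will be fitted with an appropriate model". The default is explicit: "We will assume a cubic polynomial model". At least one other model form is to be computed as a check, and a more complex approach such as state-space is to be considered if results depend on the model. No time window is given for the fit.
- **Tracer.** Section III.C, in the paragraph on the glycerol isotope study: "An 3 hours later, following consumption of the glucola/fructose mixture, 50 mg/kg of an oral" 13C-glycerol is drunk. The wording is garbled; I read it as 3 h after the glucose and fructose drink. Section IV adds: "OGTT with an oral tracer will be conducted in all subjects".
- **Sampling.** Section III.D, item 3: "An OGTT will be performed with multiple blood draws over 6.5 hours".
- **Named lipolysis model.** Section III.C also says "Lipolysis will be modeled using FFA concentrations".

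No section subtracts labelled glycerol, limits the glycerol fit to the time before the tracer, or puts a break at 3 h.

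**The concern.** Serum glycerol reflects lipolysis only while adipose tissue is the main source. After the tracer drink there is a second source, and 3.5 of the 6.5 hours of sampling follow it. If Section VII is carried out as written on total glycerol, the later part of the curve mixes lipolysis with absorption and clearance of the tracer.

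The planned safeguards address the shape of the curve, not its source. A spline, a piecewise-linear curve and a cubic fitted to total glycerol all contain the ingested part, and they can agree with one another while doing so. The Section IV check on whether 6.5 h is long enough, in the first 6 subjects, looks at glucose and insulin only, so it would not show the problem.

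There is a second, smaller effect. One smooth curve drawn across the dose lets the late rise pull on the fit before 3 h, where the data are free of tracer.

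At stake is any group comparison or correlation that treats the fitted glycerol curve as lipolysis. Because the dose scales with total body weight, the ingested part could differ systematically with body size.

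**Working it through.** The plan states no figure on this point, so there is none to reproduce. From the documents come the dose (50 mg/kg), its time (3 h), the length of the test (6.5 h) and the eligible weight range (84–325 lb). All kinetic values and curve shapes below are assumptions.

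**1. Dose.** 84 lb × 0.4536 = 38.1 kg and 325 lb × 0.4536 = 147.4 kg, so 50 mg/kg is 1.9 to 7.4 g. Per kg it is 50/95.07 × 1000 = 526 µmol (molar mass assumed for fully labelled glycerol) or 50/92.09 × 1000 = 543 µmol (unlabelled). If endogenous appearance is assumed to be 1–4 µmol/kg/min, then over 3.5 h (210 min) it totals 210–840 µmol/kg. The swallowed dose is thus 526/840 = 0.6 to 543/210 = 2.6 times the endogenous amount. How much of it reaches peripheral blood is not given.

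**2. Varying the share S of the dose that reaches the circulation.** Assumed endogenous curve (µmol/L, t in h): 40 + 60·exp(−t/0.5) + 50/(1 + exp(−(t−5)/0.5)), which starts at 100. Its area is 150 over 0–3 h and 216 over 3–6.5 h (µmol·h/L). The tracer is one-compartment with ka = 2/h, ke = 1.5/h and V = 0.3 L/kg. Its area over 3–6.5 h is

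S × (526/0.3) × 2/(2 − 1.5) × [(1 − e^−5.25)/1.5 − (1 − e^−7)/2] = S × 1753 × 4 × 0.1636 ≈ 1147·S.

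A least-squares cubic is fitted over 0–6.5 h to samples at 0, 10, 20, 30, 45, 60 and 90 min and every 30 min thereafter.

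| S | Tracer peak | True total, 3–6.5 h | Cubic, 3–6.5 h | Cubic vs endogenous 216 | Cubic, 0–3 h (true 150) |
|---|---|---|---|---|---|
| 0 | 0 | 216 | 218 | +1% | 147 |
| 2% | 15 | 239 | 238 | +10% | 150 |
| 5% | 37 | 273 | 267 | +24% | 155 |
| 10% | 74 | 331 | 317 | +47% | 162 |
| 25% | 185 | 503 | 464 | +115% | 185 |
| 50% | 370 | 790 | 711 | +229% | 223 |

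Over the whole test at S = 5%, the true total is 150 + 273 = 423 and the cubic gives 155 + 267 = 422. At S = 50% the figures are 940 and 934. The cubic recovers the total area well. It moves part of that area back across the dose, into 0–3 h.

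**3. Varying the tracer peak relative to fasting.** Assumed parabola 30 + 70·((t − 3.25)/3.25)²: fasting 100, nadir 30, back to 100 at 6.5 h. Its area is 30 × 6.5 + 70 × 6.5/3 = 346.7. A cubic fits it exactly, so any error comes from the tracer. With absorption half-life 0.25 h and elimination half-life 0.5 h, the unit curve 2^(−u/0.5) − 2^(−u/0.25) peaks at 0.25 and has area 0.355 over 3.5 h. A peak P therefore adds P × 0.355/0.25 = 1.42·P. Cubic fitted to half-hourly samples:

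| Peak, % of fasting | Tracer area | True total over endogenous | Cubic over endogenous | Cubic error, 0–3 h |
|---|---|---|---|---|
| 5 | 7.1 | +2.0% | +2.0% | +0.6% |
| 10 | 14.2 | +4.1% | +3.9% | +1.1% |
| 50 | 71.0 | +20.5% | +19.7% | +5.5% |
| 200 | 284 | +81.9% | +78.9% | +22.1% |

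With an elimination half-life of 1 h on the same curve, the true excess is 2.9%, 5.8%, 29% and 117%, and the 0–3 h error is 0.4%, 0.9%, 4.3% and 17%.

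Across several assumed endogenous shapes with these fasting and nadir values, the whole-test excess is about 2–6% for peaks of 5–10% of fasting and about 17–110% for 50–200%. The 0–3 h error is about 1–2% and about 5–26%. The cubic stays within about 4% of the true total area. The ends of these ranges move by several points with the shape chosen.

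**The case against.** The best defence is that the only lipolysis model the plan names uses FFA, which the tracer does not supply. Glycerol is then an additional marker. The fit window is unstated, another model form is required, and the lab table sends glycerol samples to tracer analysis, so a label correction may be intended. Most of this stands, and it limits the impact. It does not remove the point: glycerol is still listed for lipolysis and still fitted, and silence on correction leaves the analyst free to fit total glycerol.

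Some stronger readings are tempting, but the documents do not support them:

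- **That the plan prescribes one cubic over 0–6.5 h.** This is the natural reading, but the window is not written down.
- **That the cubic inflates the area.** Nearly all of the excess is the tracer itself. Only the 0–3 h distortion comes from fitting one curve across the dose.
- **That adipose IR, and so the hepatic-fat regression in Section VII, is biased.** The documents do not say whether adipose IR uses glycerol or FFA.
- **That Aim 2 must drop glycerol.** Its hypothesis that profiles "will differ the most between 3-6 hours" does cover a period that opens with the dose, but the likely targets it names are FFA and DNL markers, not glycerol.
- **That unlabelled glycerol is already available.** The isotopomer analysis described is of serum glucose. A measured labelled-glycerol concentration is not established.

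**Conclusion.** The concern holds for a secondary marker. If Section VII is followed as written on total glycerol, values after 3 h combine endogenous and ingested glycerol and cannot be read as lipolysis, whichever curve is used. A single smooth curve across the dose can also distort the clean 0–3 h data.

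The direction after 3 h follows from the documents: ingested glycerol can only add to the total. The size does not. It rests on the assumed share of the dose reaching the circulation, the endogenous curve, the kinetics and the sampling times. At a tracer peak of 5–10% of fasting the effect is small; at 50–200% it would dominate the later part of the curve. The area summaries used here only gauge size, since the plan does not name glycerol AUC as an outcome.

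The primary outcome, pathway activity from the isotopomer analysis, is unaffected, as is the FFA-based lipolysis model.

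**What to change.** In Section VII, under curve fitting, state that:

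1. Glycerol-based lipolysis is derived from a fit to the 0–3 h samples drawn before the tracer.
2. Total glycerol after 3 h is not used as a measure of lipolysis.
3. FFA remains the lipolysis model for the full 6.5 h.
4. If, and only if, labelled glycerol is already quantified in the tracer samples, unlabelled glycerol (total minus labelled) may be used after 3 h, with a break in the curve at 180 min. The break alone is not enough, because it changes the shape of the fit and leaves the ingested glycerol in.

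The first three items are wording only and need no new assay, visit or participant. The cost is fewer points per fit and no late-phase glycerol measure. The protocol does not list the draw times, so the sponsor should confirm that there are enough pre-tracer samples for a four-parameter cubic, and that any 3 h sample is taken before the tracer drink. Item 4 could need an added assay if labelled glycerol is not already measured.

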Rationale: Altered glucose and fat metabolism is most apparent in the post-prandial state, in terms of insulin resistance, β-cell failure, hyperglycemia and DNL. Our preliminary data indicates that glucose and insulin concentrations are most different between 3-4 hours following a glucose load.

The optimal timing post-drink to describe metabolomics differences is not known.

Methods: Targeted metabolomics profiles will be performed at intervals during the OGTT to determine time points that provide the biggest difference in girls with HS, hyperglycemia, inadequate β-cell response and IR. Specific targets will likely be free fatty acid and DNL markers, and will be determined from on ongoing pilot study.

II. Background and Significance:

a) Overall background:

Polycystic Ovarian Syndrome (PCOS) affects 6-10% of U.S. women, with an estimated economic burden of \$4 billion, and is increasing in prevalence in parallel with the obesity epidemic^{1,2}. PCOS includes elevated androgens, and higher rates of insulin resistance (IR), type 2 diabetes (T2D), nonalcoholic fatty liver disease (NAFLD) and cardiovascular disease (CVD)³⁻⁶. The increasing rates of obesity-related PCOS are a major contributor to the earlier onset and rising incidence of T2D, NAFLD and CVD³⁻⁷. Current PCOS therapies are marginally efficacious, and one of them, oral contraceptives, may adversely affect CVD risk⁸⁻¹⁴. *Despite the high prevalence and serious morbidity associated with PCOS, a gap exists in the current therapeutic options.*

b) Mechanisms of insulin resistance in PCOS

Alterations in hepatic metabolism may be central to IR and cardiometabolic disease in PCOS.

[figure not shown]
An estimated 50-70% of obese women with PCOS have NAFLD, compared to 20-30% of obese women without PCOS ^{7,15}. Furthermore, obese women with PCOS and NAFLD are more IR than those without NAFLD, indicating a link between NAFLD and worsening IR in PCOS ⁴. Liver enzyme concentrations, as a marker of NAFLD, independently predict dysglycemia and T2D onset¹⁶, and a new NAFLD medication decreased dysglycemia¹⁷, arguing for a tight connection between glycemia and liver health. In obese non-PCOS youth, NAFLD correlates with adipose, hepatic and muscle IR, is worsened by fructose consumption, and reversed by weight loss¹⁸⁻²¹. Animal models of primary

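### Aim 2 selects the times with the largest observed differences, with no formal test of its 3–6 h hypothesis and no allowance for the selection

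*Combined protocol and SAP*

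**What the plan says.** Section I gives the objective as "Aim 2: Describe the optimal timing for identifying metabolomics profiles associated with risk for T2D and HS", with a directional hypothesis: "Metabolomics profiles between girls with HS and worse IR will differ the most between 3-6 hours". The Aim 2 methods say that "Targeted metabolomics profiles will be performed at intervals during the OGTT", the purpose being "to determine time points that provide the biggest difference in girls with HS, hyperglycemia, inadequate β-cell response and IR". Neither the sampling times nor the metabolite list is fixed: "Specific targets will likely be free fatty acid and DNL markers, and will be determined from on ongoing pilot study". The evidence behind the window is that "glucose and insulin concentrations are most different between 3-4 hours following a glucose load", which concerns glucose and insulin and covers only part of 3–6 h.

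Section VII (Metabolomics data) has three sentences. Targeted concentrations are compared between groups, results are set against the isotopomer findings, and, for timing, "Changes in metabolites over time will be compared between groups, to determine the times that demonstrate the largest differences". The groups are not named there. No contrast for the window, repeated-measures model, multiplicity rule, interval for the chosen time or validation step is given. Section III.A lists targeted metabolomics as a secondary outcome and attaches the word exploratory to the untargeted analysis. Section VII uses that word only for the microbiota.

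**The concern.** The hypothesis is about a window fixed in advance, but the analysis rule is a search for a maximum. A search always returns a best time, whether or not one exists. The difference reported at that time combines a true difference with the noise that made it the largest, so on average it is too big. Whether the peak happens to lie in 3–6 h then becomes the only evidence on the hypothesis, with no stated standard for judging it.

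The data are meant to inform grant applications for treatment trials (Section III.E) and to refine the protocol (Section VIII). An inflated effect at an unstable time could mislead later sampling schedules and sample sizes.

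**Working it through.** **Plan's own figure.** There is none for Aim 2. The stated powers concern hepatic flux, and they reproduce by two-sided t test: 0.977 against 0.97 (15 v 15), 0.869 against 0.87 (20 v 20) and 0.871 against 0.87 (30 v 15).

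**Inputs.** All are assumptions except where a source is named.
- Samples: K = 5, 8 or 14 equally spaced times over 0–6.5 h.
- Within-girl correlation: AR(1) with ρ = 0.5 or 0.8; SD 1 at each time.
- Group size: 15 per group, borrowed from the flux power calculation in Section VII, and 30 per group for larger pooled groups. The enrolment table plans 80 tracer OGTTs.
- One metabolite and one phenotype contrast. The time with the largest absolute group difference is picked. 10,000 simulated trials per scenario.

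**Step 1: noise at one fixed time, no true difference.** The standard error of the group difference is √(2/15) = 0.365 SD. The expected absolute difference is 0.365 × √(2/π) = 0.365 × 0.798 = 0.29 SD, which the simulation also gave. Picking the largest of K such differences can only raise this.

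**Step 2: chance share of the window.** The grid steps are 6.5/4 = 1.625 h, 6.5/7 = 0.93 h and 6.5/13 = 0.5 h. The samples lying in 3–6 h are therefore 2 of 5 (0.40), 3 of 8 (0.38) and 7 of 14 (0.50).

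**Step 3: two truths, 15 per group.** Flat means 0.5 SD at every time. Peak means a true maximum of about 0.8 SD near 4.5 h. Differences are in true SD units.

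| K | ρ | Flat: difference at picked time | Flat: picked in 3–6 h | Peak: observed / true at picked time | Peak: exact best time picked | Peak: picked in 3–6 h | Ratio, peak to flat |
|---|---|---|---|---|---|---|---|
| 5 | 0.5 | 0.85 | 0.37 | 0.88 / 0.62 | 0.58 | 0.78 | 2.1 |
| 5 | 0.8 | 0.75 | 0.34 | 0.82 / 0.66 | 0.71 | 0.84 | 2.5 |
| 8 | 0.5 | 0.95 | 0.36 | 0.99 / 0.63 | 0.38 | 0.77 | 2.1 |
| 8 | 0.8 | 0.84 | 0.32 | 0.90 / 0.65 | 0.47 | 0.81 | 2.5 |
| 14 | 0.5 | 1.07 | 0.49 | 1.11 / 0.64 | 0.21 | 0.85 | 1.7 |
| 14 | 0.8 | 0.95 | 0.46 | 1.00 / 0.64 | 0.24 | 0.84 | 1.8 |

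The last column divides the two window probabilities, for example 0.78/0.37 = 2.1. Seeing the peak inside 3–6 h is thus only about twice as likely under a real peak as under no best time at all.

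**Step 4: group size.** When differences are divided by each sample's own pooled SD, as would be reported, the flat 0.5 SD shows as 0.79–1.14 SD with 15 per group and 0.69–0.93 SD with 30. The inflation factors are 0.79/0.5 = 1.6 to 1.14/0.5 = 2.3, and 0.69/0.5 = 1.4 to 0.93/0.5 = 1.9. The picked time lies in 3–6 h in 32–48% of trials.

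**Step 5: candidate tests of the window.** On the same AR(1) data with no group-by-time effect, a late-minus-early contrast from a model with only a random intercept rejected in 8–34% of trials at a nominal 5%. A per-girl contrast compared by t test rejected in about 5%.

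**The case against.** Aim 2 is worded as description, metabolomics is secondary, and nothing promises a confirmatory claim or a clinical use of the chosen time. This stands: strict family-wise control is not required. It does not remove the point, because the aim carries a directional hypothesis, the targeted analysis is not labelled exploratory, and a descriptive estimate of a best time still needs its uncertainty.

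A second objection is that the size depends on inputs the documents do not give, and that 15 per group belongs to another comparison. This also stands. With larger pooled groups the inflation shrinks but does not vanish.

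A reader might infer a high false-positive rate. If each time were tested at p<0.05, one metabolite with no true difference would give at least one hit in 13–47% of simulated trials with 15 per group, and more metabolites would raise this. The plan states neither per-time tests nor a threshold for metabolomics, and it does not give the number of metabolites. These rates therefore describe an analysis that the plan does not specify.

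**Conclusion.** The point holds as a cheap improvement. The plan states a selection rule, gives no formal test of the 3–6 h hypothesis and makes no allowance for selection. Under the assumed grids and correlations, a flat 0.5 SD difference is reported as about 0.8–1.1 SD (15 per group) or 0.7–0.9 SD (30 per group). A peak inside the window occurs by chance in about one third to one half of trials, close to the share of samples taken there. Several metabolites and four phenotype contrasts would add to the selection effect.

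Two stronger readings are not supported. A reader might infer that the chosen time is itself biased. What follows from the rule is that the time is unstable and reported without an interval; the upward bias is in the effect. A reader might also infer that the hypothesis goes unexamined. Comparing trajectories between groups does allow an informal look at where the differences peak; what is missing is a formal test.

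**What to change.** Before analysis, fix the sampling times, the targeted metabolites and the groups for each phenotype contrast. Then:

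- **Test the hypothesis directly.** For each metabolite, compute for each girl the mean of the 3–6 h samples minus the mean of the samples before 3 h. Assign the 3 h and post-6 h samples in advance; the glycerol tracer is also given at about 3 h. Compare the contrast between groups by t test, or by regression with the OSA adjustment already planned in Section VII. A mixed model is an alternative if its covariance is unstructured or serial; a random intercept alone is not enough.
- **Show both windows.** The hypothesis concerns the size of the difference, while the contrast is signed. Report the group difference in each window so that a sign reversal is not read as support.
- **Control the false discovery rate** across metabolites and phenotype contrasts.
- **Report the best time as hypothesis-generating**, with a bootstrap that repeats the selection in each resample and a selection-corrected (bootstrap or cross-validated) effect at that time.

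The cost is SAP wording, modest extra analysis and fewer nominal hits. No new participants, visits or blood samples are needed.
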